7.1 SAMPLE SIZE CALCULATION

The sample size calculation for this study was based on the primary outcome of ulcer healing. The ESCHAR trial was a similar randomised study, which published the final results in 2007 (see 1.1.3). A total of 500 patients with open or recently healed venous ulcers were randomised to standard therapy alone or standard therapy plus open surgery for superficial venous reflux. The study was powered and designed to evaluate differences in ulcer recurrence (rather than healing).

Consequently, the median time from randomization to treatment delivery was over 7 weeks. Nevertheless, the 24-week healing rate in patients randomised to standard treatment (compression alone) was approximately 60%. Two recent prospective studies evaluating the early treatment of superficial venous reflux suggested that the 24-week healing rate may be as high as 82%^{24 25}.

In order to calculate a sample size for this study, a benefit associated with early treatment is estimated at around 15%. Assuming the 24-week healing rate in the standard arm is 60%, to identify a difference in 24-week healing rates of 15% between the two groups (60% vs 75%) with 90% power and allowing for 10% dropout the study will therefore require 416 subjects (208 in each arm, 254 healed leg ulcers in total). To incorporate further allowances for protocol violations and unexpected dropouts, the target sample size will be 450 patients.

Assuming a 15% drop out rate for the study and that 90% of primary ulcers eventually heal, it is estimated that >340 of the recruited 450 patients will be eligible for inclusion in the ulcer recurrence analysis. With this number of participants, and allowing for the healing rates (of the index ulcer prior to entry into this analysis of ulcer recurrence) to differ by up to 20% between the two study arms, the study extension will have at least 80% power to detect a difference of 15% or more in ulcer recurrence rates between the two arms at the 5% significance level.

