### **4.4 Primary Endpoints**

The primary outcome is time to complete healing and we will test the hypothesis that there is no difference in this between the control and intervention groups using a Cox model with study centre as a random effect (Table 6). Kaplan-Meier survival curves and the log-ran test will also be presented (Figure 3). As a subsidiary analysis we will investigate the effect of potential confounders listed in section 2.1 (age, ulcer chronicity and ulcer size) on the treatment effect and on time to complete healing using Cox regression, again with centre included in the Cox regression analysis as random effect (Table 6). To assess whether the treatment effect is consistent across all patient sub-groups, the hazard ratios and 95% confidence intervals for treatment from the above Cox regression models (with adjustment for potential confounders and centre as a random effect) will be re-calculated for each of the following subgroups separately; BMI (<23, 23.0-25.0, 25.01-30.0, > 30), Age ( $\leq 49$ , 50-69, 70+), gender (male, female), smoking (Never, previous, current), ulcer size (by quartile), ulcer duration (by quartile), history of deep vein thrombosis (yes, no), history of rheumatoid arthritis (yes, no), taking anti-platelet therapy (yes, no), history of intervention on previous leg ulcer (yes, no intervention, no previous ulcer) and baseline EQ5D (by quartile). The results will be presented using a Forest plot (Figure 4), with the overall result also included at the bottom. We will also use Cox regression to look for differences between the treatment arms by type of endovenous treatment (Endothermal alone, Foam sclerotherapy alone, Mechanochemical alone (MOCA), Endothermal plus Foam, or MOCA plus Foam). Results (hazard ratios and 95% confidence intervals will also be presented graphically in the Forest plot (Figure 5). These subsidiary analyses are intended to provide reassurance that the observed treatment effect is consistent across all patient sub-groups. The study is not powered to detect differences between sub-groups and any observed patterns should be interpreted extremely cautiously, owing to the smaller numbers and increased chance of Type I error. For Cox regression models the proportionality assumption will be assessed graphically (using diagnostic plots) and using Grambsch and Therneau tests and overall fit will be assessed graphically by plotting the Nelson-Aalen cumulative hazard function versus the Cox-Snell residuals and comparing to a 45°reference line.

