To assess whether the treatment effect on ulcer free time is the same across all patient subgroups, the coefficients and 95% confidence intervals for the treatment effect from the above multiple linear (or ordinal) regression model (based on study participants with follow up of at least 1 year) will be re-calculated for each of the following subgroups separately; BMI (<23, 23.0-25.0, 25.01-30.0, > 30), age ( $\leq$ 49, 50-69, 70+), gender (male, female), smoking (Never, previous, current), ulcer size (by quartile), ulcer duration (by quartile), history of deep vein thrombosis (yes, no), history of rheumatoid arthritis (yes, no), taking anti-platelet therapy (yes, no), history of intervention on previous leg ulcer (yes, no intervention, no previous ulcer) and baseline EQ5D (by quartile). The results of this subgroup analysis will be presented in a Forest plot with the overall result also included at the bottom (Figure 6). Differences between the treatment arms by type of endovenous treatment (Endothermal alone, Foam sclerotherapy alone, Mechanochemical alone (MOCA), Endothermal plus Foam, or MOCA plus Foam) will also be investigated and the results (model coefficients and 95% confidence intervals) will be presented graphically in the Forest plot (Figure 7). These subsidiary analyses are intended to provide reassurance that the observed treatment effect is consistent across all patient subgroups. The study is not powered to detect differences between sub-groups and any observed

patterns will be interpreted extremely cautiously, owing to the smaller numbers and increased chance of Type I error.

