Pathophysiologic dysfunction		
Reflux		
Obstruction		
Both		
No venous cause		
VCSS Score		
Palpable pedal pulses		
Yes		
No		

\* Data presented as frequency (percentage) for categorical variables and median (range) for continuous variables

†A patient can have both deep vein reflux and obstruction

Table 5 Treatment summary

	EVRA N=	Standard N=
Endothermal only		
Foam only		
Mechanochemical ablation (MOCA) only		
Endothermal and Foam		
MOCA and Foam		

\* *Data presented as frequency (percentage)*

Table 6 Time to ulcer healing in patients with chronic venous ulceration (Cox regression model)

	Univariate model*		Multivariate model†	
	HR (95% CI)	P value	HR (95% CI)	P value
Treatment				
Standard arm				
EVRA				
Age (yrs)				
Ulcer chronicity (mths)				
Ulcer size				
1 st Quartile				
2 nd Quartile				
3 rd Quartile				
4 th Quartile				

\* Adjusted by centre (centre included in the model as a random effect)

† Adjusted by centre, age, ulcer size and chronicity (centre included in the model as random effect and age, ulcer size and chronicity as fixed effects).

Table 7 Summary of 12-week and 24-week ulcer healing rate and ulcer free time\*

	EVRA N=	Standard N=
12-week ulcer healing rate		
24-week ulcer healing rate		
No. of patients with recurrent ulcer		
Ulcer free time		

\* Data presented as frequency (percentage) for categorical variables and median (range) for continuous variables

Table 8 Multiple linear regression (ordinal regression) for ulcer free time (days) to 1 year in patients with chronic venous ulceration

	Univariate model*		Multivariate model†	
	Coefficient (95% CI)	P value	Coefficient (95% CI)	P value
Treatment				
Standard arm				
EVRA				
Age (yrs)				
Ulcer chronicity (mths)				
Ulcer size				
1 st Quartile				
2 nd Quartile				
3 rd Quartile				
4 th Quartile				

\* Adjusted by centre (centre included in the model as a random effect)

† Adjusted by centre, age, ulcer size and chronicity (centre included in the model as random effect and age, ulcer size and chronicity as fixed effects).

Table 9 Summary of quality of life (AVVQ, EQ-5D, SF36) at baseline, 6 weeks, 6 months and 12 months after randomisation

	N	EVRA	Standard
		Mean (SD)	Mean (SD)
AVVQ			
Baseline			
6 weeks			
6 months			
12 months			

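### Consistency of effect across 11 factors is to be judged from 33 separate refits per outcome with no interaction test, and the modality plots need a stated comparator set and a selection caveat

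*SAP*

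**What the plan says.** **Subgroups (Figures 4 and 6).** SAP 4.4 takes hazard ratios from the Cox model "with adjustment for potential confounders and centre as a random effect" and says that they "will be re-calculated for each of the following subgroups separately". It then lists 11 factors. SAP 4.5 does the same for ulcer free time with linear or ordinal regression and gives the purpose as "To assess whether the treatment effect on ulcer free time is the same across all patient subgroups". SAP 4.4 describes these analyses as "intended to provide reassurance that the observed treatment effect is consistent across all patient sub-groups". Both sections add that the trial is not powered for subgroup differences, and they ask for great caution because of small numbers and Type I error.

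**The model being refitted.** The note to Table 6 describes it as having "centre included in the model as random effect and age, ulcer size and chronicity as fixed effects". Tables 6 and 8 enter ulcer size as quartiles. Neither table has an interaction row, and neither document plans an interaction or heterogeneity test. SAP 2.1 and 4.4 speak of examining how confounders bear on the treatment effect, but Table 6 shows that this means adjustment by main effects.

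**Modality (Figures 5 and 7).** SAP 4.4 will "look for differences between the treatment arms by type of endovenous treatment", over five classes. SAP 4.5 has the parallel analysis: "Differences between the treatment arms by type of endovenous treatment". Protocol 5.2 leaves the procedure to the treating clinician, patient by patient. Protocol 5.4 lets standard-arm patients have ablation after confirmed healing, at 6 months, or on clinical deterioration. SAP Table 5 tabulates modality in both arms.

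**The concern.** Whether an effect is consistent is a question about differences between levels. A set of separate estimates, each with its own interval, does not test those differences, so the reader is left to compare points and intervals by eye. Under a fully consistent effect the points will still scatter, and some intervals will cross 1 while others do not. The plots are meant to reassure, yet they could suggest effect modification that is only chance.

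Separate refitting also re-estimates every covariate in every level. Inside an ulcer-size quartile the quartile terms are constant and cannot be estimated, so the model cannot be run there as specified. Small levels may give unstable fits.

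For modality, the early-arm classes are formed by clinical choice after randomisation. A reader could credit a modality with a difference that comes from the kind of patient who receives it. The printed caution covers small numbers and Type I error but not selection.

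**Working it through.** **1. Count of refits.** BMI 4, age 3, gender 2, smoking 3, ulcer size 4, ulcer duration 4, deep vein thrombosis 2, rheumatoid arthritis 2, anti-platelet therapy 2, previous intervention 3, EQ5D 4. The sum is 33 levels per outcome, or 66 over Figures 4 and 6. One interaction test per factor would use 33 − 11 = 22 degrees of freedom in 11 tests.

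**2. The plan's own figure.** Protocol 7.1 assumes 60% against 75% healed at 24 weeks, 90% power, 10% dropout, and "254 healed leg ulcers in total" from 416 patients.
- HR = ln(0.25)/ln(0.40) = 1.513.
- Freedman's formula, two-sided 5%: events = (1.960 + 1.282)² × (2.513/0.513)², which gives 253 (stated 254).
- 253/0.675 = 375, or 188 per arm (376). 376/0.9 = 418 (stated 416).

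So 254 is in effect the 24-week count: 375 × 0.675 = 253.

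**3. Events at one year.** SAP 4.9 censors at one year. Assuming constant healing rates:
- Standard: 1 − 0.40^(52/24) = 86.3%. Early: 1 − 0.25^(52/24) = 95.0%. Mean 90.7%.
- 416 less 10% is 375 patients, giving 340 healings. 450 less 10% is 405 patients, giving 367.

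**4. Chance spread over four quartiles, true HR 1.513 in each.** SE of a quartile log HR = 2/√(E/4). The range of four independent normal estimates was simulated (2,000,000 draws).

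| Healings E | SE | Median largest/smallest HR | Chance ratio exceeds 2 |
|---|---|---|---|
| 340 | 0.217 | 1.54 | 11% |
| 367 | 0.209 | 1.51 | 9% |
| 254 (24-week count) | 0.251 | 1.64 | 21% |

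Power within one quartile is 48% (340) or 51% (367). The chance that at least one of the four intervals includes 1 is therefore 1 − 0.48⁴ = 95% or 1 − 0.51⁴ = 93%, although the effect is identical throughout.

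**5. Refitting in small levels.** The Table 6 model has six fixed coefficients (treatment, age, chronicity, three for ulcer size) plus centre. The documents give no level sizes apart from the quartiles. In simulations of 375 and 405 patients with assumed covariate effects and no centre effect, true HR 1.513, the mean HR was:
- 25% level: 1.54–1.56 from separate fits, 1.52–1.53 from one interaction model.
- 10% level: 1.63–1.65 against 1.53–1.55.
- 5% level: 1.76–1.81 against 1.52–1.54, with 8–11% of separate fits failing.

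**6. What an interaction test can do.** For a two-level factor with a share p in one level, SE = √(4/(Ep) + 4/(E(1−p))). For a ratio of HRs of 1.51:
- 50/50 split: SE 0.217 or 0.209; power 48% or 51%.
- 90/10 split: SE 0.362 or 0.348; power 21% or 22%.

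Eleven independent tests at 5%: 1 − 0.95¹¹ = 43% chance of at least one false positive.

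**7. Modality, by text.** The SAP compares the arms, so the standard arm is the implied comparator. It does not say whether each class faces all standard-arm patients or only those later given the same modality. Because Protocol 5.4 links standard-arm ablation to healing or deterioration, splitting that arm by ablation would partly select on the outcome. Using the whole arm avoids this, but the early-arm class is still chosen by the clinician. Protocol 5.2 and 6.4.1 tie further treatment to the 6-week scan, and the SAP does not say whether that changes a patient's class.

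**The case against.** The strongest reply is that these analyses are labelled subsidiary and already carry a clear warning about power and Type I error. That stands as a limit on the harm, but a warning does not supply the missing test.

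A reader might infer that chance variation between levels cannot be weighed at all. The documents do not support that. Each level has a 95% CI, the overall result is on the plot, and the levels of a factor are disjoint, so a heterogeneity statistic could be worked out from the figure. What is missing is a pre-specified test.

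A reader might also take the 21% figure as the main size. It uses the 24-week count, whereas follow-up runs to one year, so 9–11% is the relevant range.

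Nor do the documents show that separate refits are materially biased. At the quartile level, the only size they fix, the two approaches nearly agree. The larger departures need assumed levels of 5% or 10% and assumed covariate effects.

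Finally, interaction tests here have low power and there are 11 of them per outcome. That is fair, and it has to be stated beside the results. They are still the direct answer to the question that the SAP asks.

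**Conclusion.** The point holds as a cheap improvement to subsidiary analyses. The plan asks about consistency and specifies no test of it. With 340–367 healings and one common effect, quartile hazard ratios would differ by a factor of about 1.5 in the median trial and by more than 2 in 9–11%. This rests on the planning rates, constant hazards, equal quartiles and no covariate effects. It concerns time to healing; no size has been worked out for ulcer free time (Figures 6 and 7). The ulcer-size quartile refit cannot be run as Tables 6 and 8 specify the model.

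On modality, two gaps remain: the comparator set is not stated and selection is not mentioned. A reader might infer that Figures 5 and 7 will be badly distorted. The documents do not support that. Illustrative shifts from 1.51 to 1.42 or 1.62 need standard-arm patients to be split by ablation, which the SAP does not say, and invented uptake rates. With all standard-arm patients as comparator, illustrative shifts for combination treatment were 0.03–0.05 in log HR against a standard error of about 0.15. The size and direction of any bias are unknown.

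The primary analysis and the sample size are not affected.

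**What to change.** **Figures 4 and 6.** For each factor, fit one model to all patients in that analysis, with the factor, treatment-by-factor terms, the planned covariates and centre. Where the factor is itself a planned covariate (age, ulcer size, ulcer duration), do not enter the same terms twice; for ulcer size the quartile terms serve as both. Take the level-specific effects and 95% CIs from this model. Report one joint interaction p-value per factor: 1 df for the four two-level factors, 2 df for the three three-level factors and 3 df for the four four-level factors. State the power from step 6, that a non-significant test does not prove consistency, and the 43% false-positive figure.

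**Figures 5 and 7.** Do not split standard-arm patients by their own later ablation. Either compare each early-arm class with all standard-arm patients, or describe modality within the early arm only. State how re-treatment after the 6-week scan is classified. Label the figures as non-randomised and open to selection bias.

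**Cost.** SAP wording and minor programming, with no new data and no change to sample size. The downside is 11 low-power tests per outcome, which must be reported as such.

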
#### 4.5 Ulcer Free Time to 1 year and 24-week Ulcer Healing Rate

Table 7 summarises the ulcer free time to 1 year and 24-week ulcer healing rate between the two arms. In the case that a patient is dead, withdrawn or lost to follow-up before 1 year, ulcer free time will be calculated as the time from randomisation until last follow-up. Multiple linear regression will be used to assess the difference between the treatments arms, with centre as a random effect, before and after adjustment for age, ulcer size and ulcer chronicity (Table 8). Graphical methods will be used to assess whether the assumption of normality is met. If the assumption of normality is not met, and there is no suitable transformation, ulcer free time will be categorized (by quartiles) and the analysis will instead be performed using ordinal regression. Model fit will be assessed using residual plots and/or goodness-of-fit tests, as appropriate. The 24-week healing rate and associated 95% confidence interval will be obtained from the Kaplan-Meier analysis (4.3). The primary analysis will be based on study participants with at least 1 year of follow up only (as explained in 2.2). As a sensitivity analysis we will repeat the above regression model (adjusted for age, ulcer size and ulcer chronicity, and centre) using all the study participants, irrespective of length of follow up.

To assess whether the treatment effect on ulcer free time is the same across all patient subgroups, the coefficients and 95% confidence intervals for the treatment effect from the above multiple linear (or ordinal) regression model (based on study participants with follow up of at least 1 year) will be re-calculated for each of the following subgroups separately; BMI (<23, 23.0-25.0, 25.01-30.0, > 30), age ( $\leq$ 49, 50-69, 70+), gender (male, female), smoking (Never, previous, current), ulcer size (by quartile), ulcer duration (by quartile), history of deep vein thrombosis (yes, no), history of rheumatoid arthritis (yes, no), taking anti-platelet therapy (yes, no), history of intervention on previous leg ulcer (yes, no intervention, no previous ulcer) and baseline EQ5D (by quartile). The results of this subgroup analysis will be presented in a Forest plot with the overall result also included at the bottom (Figure 6). Differences between the treatment arms by type of endovenous treatment (Endothermal alone, Foam sclerotherapy alone, Mechanochemical alone (MOCA), Endothermal plus Foam, or MOCA plus Foam) will also be investigated and the results (model coefficients and 95% confidence intervals) will be presented graphically in the Forest plot (Figure 7). These subsidiary analyses are intended to provide reassurance that the observed treatment effect is consistent across all patient subgroups. The study is not powered to detect differences between sub-groups and any observed

patterns will be interpreted extremely cautiously, owing to the smaller numbers and increased chance of Type I error.

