7.3 MISSING, UNUSED AND SPURIOUS DATA

There will be no data imputation for missing data in the primary endpoint (time to healing) and the secondary endpoint of ulcer free time. Any imputation methods used may be proposed for purposes of sensitivity analysis for other secondary outcomes, including ulcer healing rate, QoL and markers of clinical success. Imputation methods will be fully documented in the SAP.

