## **2.2 Definition of Population for Analysis**

The study population will comprise all participants who were randomised. A secondary per-protocol analysis will also be carried out after excluding patients with protocol violations. For the analysis of ulcer free time, the population for analysis will be patients with complete follow-up data only. This is because ulcer free time to one year depends on the time of primary ulcer healing and duration of recurrent ulcer (for example, patients with ulcer free time of 0 day may have an unhealed primary ulcer at 1 year follow-up, or may have withdrawn from the study after healing at month 1, or may have withdrawn from the study after healing at month 11). By adding this constraint some bias may have been introduced (as the analysis will have been based on complete cases only) but ulcer free time will have only one interpretation. As a

sensitivity analysis, the analysis of ulcer free time will therefore be repeated using all the patients, irrespective of length of follow up. This should give a very conservative estimate of the treatment effect.

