#### **4.9 Derived Variables**

1. Deep vein reflux is defined as iliac, femoral, popliteal or crural deep vein reflux detected by Duplex scan.
2. Deep vein obstruction is defined as iliac, femoral, popliteal or crural deep vein outflow obstruction detected by Duplex scan.
3. Time to ulcer healing will be calculated as the difference between the final healing date and date of randomisation. Final healing date is collected in the InForm database and this variable is entered by trial manager after experts agree on the healing date. Patients will be censored at the time of last follow-up if they are dead, withdrawn or lost to follow-up before primary ulcer healing. The follow-up time is one year after randomisation and thus patients with unhealed primary ulcer at one year after randomisation will be also censored.
4. One-year ulcer free time will be calculated as total follow-up time in days (i.e. one year or time to the last follow-up if patients are dead, withdrawn or lost to follow before one year) deducting the total duration of ulcers, including primary ulcer and recurrences.
5. Ulcer chronicity will be calculated as the difference between the date of current ulcer appeared and the date of randomisation.

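### SAP 4.5 and 4.9 define ulcer free time for early leavers in incompatible ways, and the all-patient sensitivity analysis is called very conservative although its direction depends on dropout by arm

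*SAP*

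**What the plan says.** SAP 4.5 gives a rule for early leavers, meaning death, withdrawal or loss within the year. For them, "ulcer free time will be calculated as the time from randomisation until last follow-up". SAP 4.9 item 4 defines the same variable for everyone, early leavers included: "One-year ulcer free time will be calculated as total follow-up time in days", where follow-up ends at one year or at the last contact, "deducting the total duration of ulcers, including primary ulcer and recurrences".

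SAP 2.2 restricts the main analysis of ulcer free time to patients with complete follow-up and concedes that this may introduce bias. It then plans to repeat the analysis in all patients, whatever their length of follow-up, and says: "This should give a very conservative estimate of the treatment effect". SAP 4.5 specifies that repeat as the same regression, adjusted for age, ulcer size, chronicity and centre. Length of follow-up is not in the model. Protocol 7.3 and SAP 2.4 rule out imputation for this endpoint.

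**The concern.** There are two linked problems.

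- **Definition.** Everyone enters with an open ulcer, so the two rules differ for every early leaver with any follow-up. A programmer working from the endpoint's own section would count ulcerated days as ulcer-free.
- **Direction.** Even with the 4.9 formula, days after a patient leaves add nothing to that patient's score. The arm with more dropout is pulled down. If that is the standard arm, the estimate moves in favour of early treatment, while the SAP tells the reader it is conservative.

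The all-patient repeat is the only analysis specified to probe the complete-case bias that SAP 2.2 admits. The per-protocol analysis in SAP 5 does not address it. If the repeat is mis-scored or its direction misread, readers may be reassured without grounds about a named secondary outcome.

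**Working it through.** **The two rules on the same patient**

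| Patient | SAP 4.5 | SAP 4.9 item 4 |
|---|---|---|
| Never healed, last seen day 200 | 200 | 200 − 200 = 0 |
| Healed day 150, last seen day 180, no recurrence | 180 | 180 − 150 = 30 |

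SAP 2.2 lists three kinds of patient with zero ulcer-free days. The first, "patients with ulcer free time of 0 day may have an unhealed primary ulcer at 1 year follow-up", completed follow-up, so it does not separate the rules. The other two withdrew after healing at month 1 or month 11. Under 4.5 they would score roughly 30 and 335 days. They can score 0 only under 4.9, with withdrawal at about the time of healing.

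**Inputs.** Protocol 7.1 gives 24-week healing of 60% and 75%, 10% dropout overall and 208 per arm. These are coherent: HR = ln(0.25)/ln(0.40) = 1.513; Freedman's formula at 90% power gives 253 events; 253/0.675/0.9 = 416.5, matching the stated 416 patients and, closely, 254 events. Neither document states an expected value for ulcer free time or a dropout rate by arm.

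**Assumptions.** Exponential healing, no recurrence, leaving times uniform over T = 365 days and unrelated to healing, and dropout by arm as shown.

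**Formulas.** Rate λ = −ln(1 − p)/168.

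- Completer mean = T − (1 − e^(−λT))/λ. EVRA 249.8, standard 206.7; true difference 43.1 days.
- Leaver mean under 4.9 = T/2 − 1/λ + (1 − e^(−λT))/(λ²T). EVRA 99.6, standard 78.7.
- Leaver mean under 4.5 = T/2 = 182.5 in both arms.
- Proportion of leavers still unhealed = (1 − e^(−λT))/(λT). EVRA 32%, standard 43%.

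Each leaver therefore lowers the arm total, under 4.9, by 249.8 − 99.6 = 150.2 days (EVRA) or 206.7 − 78.7 = 128.0 days (standard). Under 4.5 the figures are 67.3 and 24.2. With dropout proportions dE (EVRA) and dS (standard):

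- 4.9: difference = 43.1 − 150.2·dE + 128.0·dS
- 4.5: difference = 43.1 − 67.3·dE + 24.2·dS

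| Dropout EVRA / standard | 4.9 | 4.5 as written |
|---|---|---|
| 10% / 10% | 40.9 | 38.8 |
| 8% / 12% | 46.4 | 40.6 |
| 5% / 15% | 54.8 | 43.3 |
| 15% / 5% | 27.0 | 34.2 |

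Overstatement begins when dS/dE exceeds 150.2/128.0 = 1.17 under 4.9 (10% against 11.7%), and 67.3/24.2 = 2.78 under 4.5. A simulation with 2 million patients per arm agreed within its error (54.6 at 5%/15% against a true 42.9).

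**No true effect** (60% healing in both arms). Under 4.9 the bias is 128.0 × (dS − dE): +5.1 days at 8%/12% and +12.8 at 5%/15%. With a simulated SD of 123 to 127 days and a standard error of about 12.3 at 208 per arm, a 5% two-sided test rejects in about 7% and 18% of trials. Under 4.5 the biases are +1.0 and +2.4 days, with rejection of 5.5% at 5%/15%.

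**If leaving depends on healing** (simulation, 5% EVRA / 15% standard, truth about 43 days):

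| Who leaves | All patients, 4.9 | Complete cases |
|---|---|---|
| Hazard of leaving 3 times higher while unhealed | 54.0 | 38.0 |
| Only unhealed patients | 52.1 | 31.2 |
| Only healed patients | 56.5 | 53.4 |

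In the first scenario an estimator of time in the healed state that allows for censoring gave 43.2 days. Under no effect it gave −0.3, against +12.2 (raw 4.9) and −5.0 (complete cases).

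**The case against.** The 4.5 sentence is probably a slip: it reproduces the first half of the 4.9 formula and drops the deduction, and 4.9, under derived variables, may be what gets programmed. That is likely, but the rule as written is still wrong and sits in the endpoint's own section.

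The reach is narrow: one sensitivity analysis of one secondary outcome. This stands. The 18% rejection rate belongs to that supporting analysis, not to a trial conclusion.

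With the planned 10% dropout split equally, both formulas fall below the truth and show no bias under no effect, so the SAP's direction is then right. Overstatement needs an imbalance that the documents neither give nor suggest. This also stands, but under 4.9 a modest imbalance is enough, and in a trial with open treatment allocation equal dropout cannot be presumed.

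The all-patient result is not always worse than the complete-case one. In the table above it is further from the truth when unhealed patients leave at three times the rate, and closer when only unhealed patients leave. In both cases the two analyses bracket the truth, so the comparison has some value. When only healed patients leave, both overstate.

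Some reporting is already promised: SAP 2.4 covers the level and pattern of missing data, and SAP 4.1 a CONSORT diagram. Table 7 could be read as complete cases only, following SAP 2.2. However, "Table 7 Summary of 12-week and 24-week ulcer healing rate and ulcer free time" has one N per arm and also carries healing rates, the 24-week one taken from the Kaplan-Meier analysis, so its population needs stating.

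**Conclusion.** Both parts hold. SAP 4.5 and 4.9 contradict each other for every early leaver with any follow-up, and 4.5 as written does not measure ulcer-free time. In the illustration a standard-arm leaver averages 183 days under 4.5 and 79 under 4.9.

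The unconditional conservative claim is not justified. With equal 10% dropout the 4.9 estimate shrinks by only about 5% (40.9 against 43.1). At 5% EVRA and 15% standard it overstates by 27% (54.8/43.1 = 1.27). With those figures reversed it understates by 37% (27.0/43.1 = 0.63). The literal 4.5 formula inflates little in these cases, but its values do not mean what their name says.

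The day counts rest on the assumed healing curve, uniform leaving times, no recurrence and assumed dropout by arm. The dependence of direction on dropout by arm is the finding; the exact days are illustrative. The primary outcome, the sample size, and the main and subgroup analyses of ulcer free time are not affected.

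**What to change.** 1. Replace the early-leaver sentence in SAP 4.5 with the 4.9 item 4 formula.
2. Delete the conservative claim in SAP 2.2, or limit it to dropout that is similar between arms or higher in the EVRA arm.
3. Report length of follow-up and dropout by arm, and state which patients the ulcer free time row of Table 7 covers.
4. Preferably, make the all-randomised sensitivity analysis account for unequal follow-up, for example by inverse-probability-of-censoring weighting using baseline covariates and healing status over time, or by pseudo-values. State the handling of deaths in advance. Neither method imputes individual outcomes, so both are compatible with Protocol 7.3: "There will be no data imputation for missing data in the primary endpoint (time to healing) and the secondary endpoint of ulcer free time".

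Items 1 to 3 cost wording and one reporting line, and cure the errors as written. Item 4 is an improvement beyond that: modest programming and no new data, at the price of assuming that censoring is explained by the measured variables, including healing status.
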